5.2.4 When to Report an Event in an Expedited Manner

Some adverse events require 24-hour notification (refer to Section [5.2.6](#)). Please complete a 24-Hour Notification Report via the CTEP-AERS website (<http://ctep.cancer.gov>) within 24 hours of learning of

the event. The full CTEP-AERS report must be completed and submitted via CTEP-AERS within 5 calendar days.

If the CTEP-AERS system is down, a 24-hour notification call must be made to ECOG-ACRIN [contact]) and to NCI [contact]). Once the system is restored, a 24-hour Notification Report must be entered into the CTEP-AERS system by the original submitter of the report at the site.

When an adverse event requires expedited reporting, submit a full CTEP-AERS report within the timeframes outlined in Section [5.2.6](#).

NOTE: Adverse events that meet the reporting requirements in Section [5.2.6](#) and occur within 30 days of the last dose of protocol treatment must be reported on an expedited adverse event report form (using CTEP-AERS). For any adverse events that occur more than 30 days after the last dose of treatment, only those that have an attribution of possibly, probably, or definitely AND meet the reporting requirements in Section [5.2.6](#) must be reported on an expedited adverse event report form (using CTEP-AERS).

5.2.5 **Other Recipients of Adverse Event Reports**

DCTD/NCI will notify ECOG-ACRIN/pharmaceutical collaborator(s) of all AEs reported to FDA. Any additional written AE information requested by ECOG-ACRIN MUST be submitted to BOTH the NCI and ECOG-ACRIN.

Adverse events determined to be reportable must also be reported by the institution, according to the local policy and procedures, to the Institutional Review Board responsible for oversight of the patient.

5.2.6 **Expedited reporting for investigational agents**

Phase 2 and 3 Trials Utilizing an Agent under a CTEP IND: CTEP-AERS Expedited Reporting Requirements for Adverse Events That Occur Within 30 Days¹ of the Last Dose of Investigational Agent (CC-5013/Lenalidomide) in this Study (Arm A) OR Within 30 Days of the Last Dose of Any Protocol Treatment.

Rev. Add13

Attribution	Grade 1	Grade 2	Grade 2	Grade 3		Grade 3		Grades 4 & 5 ²	Grades 4 & 5 ²
	Unexpected and Expected	Unexpected	Expected	Unexpected with Hospitalization	without Hospitalization	Expected with Hospitalization	without Hospitalization	Un-expected	Expected

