Pregnancies and suspected pregnancies (including a positive or inconclusive pregnancy test, regardless of age or disease state) occurring while the subject is on Lenalidomide, or within 28 days of the subject’s last dose of Lenalidomide, are considered immediately reportable events. The pregnancy, suspected pregnancy, or positive/ inconclusive pregnancy test must be reported via CTEP-AERS within 24 hours of the Investigator’s knowledge. Please refer to [Appendix XIII](#) for detailed instructions on how to report the occurrence of a pregnancy as well as the outcome of all pregnancies.

3. Protocol specific expedited reporting exceptions:

For study arm A, the adverse events listed below **do not** require expedited reporting via CTEP-AERS:

- Grade 4 expected myelosuppression (unless it results in a hospitalization, in which case, a CTEP-AERS report is required).

Rev. 6/11

5.2.7

Reporting Secondary AML/MDS/ALL

All cases of second and secondary malignancies [including acute myeloid leukemia (AML) and myelodysplastic syndrome (MDS)], regardless of attribution, that occur following treatment on NCI-sponsored trials must be reported as follows:

1. Submit a completed Second Primary Form within 30 days to ECOG-ACRIN at:

ECOG-ACRIN Operations Office - Boston
FSTRF
[name]
[name]
2. Report the diagnosis via CTEP-AERS, regardless of attribution, at <http://ctep.cancer.gov>

Report under a.) leukemia secondary to oncology chemotherapy, b.) myelodysplastic syndrome, c.) treatment related secondary malignancy, or d.) Neoplasm Other, malignant (grade 3 or 4)
3. Submit a copy of the pathology report to ECOG-ACRIN and NCI/CTEP confirming the diagnosis.
4. If the patient has been diagnosed with AML/MDS, submit a copy of the cytogenetics report (if available) to ECOG-ACRIN and NCI/CTEP.

NOTE: All new malignant tumors must be reported through CTEP-AERS whether or not they are thought to be related to either previous or current treatment. All new malignancies should be reported including solid tumors (including non-melanoma skin malignancies), hematologic malignancies, Myelodysplastic Syndrome (MDS)/Acute Myelogenous Leukemia (AML), and *in situ* tumors.

Whenever possible, the CTEP-AERS report should include the following:

- tumor pathology
- history of prior tumors
- prior treatment/current treatment including duration
- any associated risk factors or evidence regarding how long the tumor may have been present

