- when and how the tumor was detected
- molecular characterization or cytogenetics or the original tumor (if available) and of any new tumor
- tumor treatment and outcome (if available). ng non-melanoma skin malignancies), hematologic malignancies, Myelodysplastic Syndrome (MDS)/Acute Myelogenous Leukemia (AML), and *in situ* tumors.

- Whenever possible, the CTEP-AERS report should include the following:

NOTE: The Second Primary Form and the CTEP-AERS report should not be used to report recurrence or development of metastatic disease.

NOTE: If a patient has been enrolled in more than one NCI-sponsored study, the Second Primary Form must be submitted for the most recent trial. ECOG-ACRIN must be provided with a copy of the form and the associated pathology report and cytogenetics report (if available) even if ECOG-ACRIN was not the patient's most recent trial.

NOTE: Once data regarding survival and remission status are no longer required by the protocol, no follow-up data should be submitted via CTEP-AERS or by the Second Primary Form.

Rev. 10/11, 7/14.
10/14, 7/16
Rev. Add13
Rev. Add14
Rev. 7/13

5.3 Comprehensive Adverse Events and Potential Risks list (CAEPR) for Lenalidomide (CC-5013, NSC 703813)

The Comprehensive Adverse Event and Potential Risks list (CAEPR) provides a single list of reported and/or potential adverse events (AE) associated with an agent using a uniform presentation of events by body system. In addition to the comprehensive list, a subset, the Specific Protocol Exceptions to Expedited Reporting (SPEER), appears in a separate column and is identified with **bold** and *italicized* text. This subset of AEs (SPEER) is a list of events that are protocol specific exceptions to expedited reporting to NCI (except as noted below). Refer to the 'CTEP, NCI Guidelines: Adverse Event Reporting Requirements' http://ctep.cancer.gov/protocolDevelopment/electronic_applications/docs/aeguidelines.pdf for further clarification. *Frequency is provided based on 4081 patients.* Below is the CAEPR for lenalidomide (CC-5013).

Rev. 7/13

NOTE: FOR THIS PROTOCOL, events listed in the SPEER column should be considered EXPECTED if the grade being reported is the same or lower than the grade noted in the parentheses next to the AE in the SPEER. Events listed in the SPEER column should be considered UNEXPECTED if the grade being reported exceeds the grade noted in parentheses next to the AE in the SPEER.

Rev. 10/14

Version 2.8, June 27, 2019¹

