¹ This table will be updated as the toxicity profile of the agent is revised. Updates will be distributed to all Principal Investigators at the time of revision. The current version can be obtained by contacting [contact]. Your name, the name of the investigator, the protocol and the agent should be included in the e-mail.

² Myocardial infarction and cerebrovascular accident (stroke) have been observed in multiple myeloma patients treated with lenalidomide and dexamethasone.

³ Graft vs. host disease has been observed in subjects who have received lenalidomide in the setting of allo-transplantation.

⁴ Infection includes all 75 sites of infection under the INFECTIONS AND INFESTATIONS SOC.

⁵ The rare adverse event of rhabdomyolysis has been observed with lenalidomide. The reports of rhabdomyolysis were confounded by concurrent use of statins and dexamethasone, concurrent viral and bacterial infections, trauma, and serotonin syndrome. Statins, infections, trauma, and serotonin syndrome are known risk factors for rhabdomyolysis.

- ⁶ There has been an increased frequency of secondary malignancies (SPM) including ALL, AML, and MDS, and certain other types of cancers of the skin and other organs in multiple myeloma (MM) patients being treated with melphalan, prednisone, and lenalidomide post bone marrow transplant. The use of lenalidomide in cancers other than MM, shows that invasive SPMs occurred in a small number of patients. Patients treated with lenalidomide should be closely followed for the occurrence of SPMs.
- ⁷ Serious tumor flare reactions have been observed in patients with chronic lymphocytic leukemia (CLL) and lymphoma.
- ⁸ A decrease in the number of stem cells (CD34+ cells) collected from patients treated with >4 cycles of lenalidomide has been reported.
- ⁹ Significantly increased risk of deep vein thrombosis (DVT), pulmonary embolism (PE), and arterial thrombosis has been observed in patients with multiple myeloma receiving lenalidomide with dexamethasone.
- ¹⁰ Gastrointestinal hemorrhage includes: Anal hemorrhage, Cecal hemorrhage, Colonic hemorrhage, Duodenal hemorrhage, Esophageal hemorrhage, Esophageal varices hemorrhage, Gastric hemorrhage, Hemorrhoidal hemorrhage, Ileal hemorrhage, Intra-abdominal hemorrhage, Jejunal hemorrhage, Lower gastrointestinal hemorrhage, Oral hemorrhage, Pancreatic hemorrhage, Rectal hemorrhage, Retroperitoneal hemorrhage, and Upper gastrointestinal hemorrhage under the GASTROINTESTINAL DISORDERS SOC.

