5.7 Duration of Follow Up

For this protocol, all patients, including those who discontinue protocol therapy early, will be followed for response until progression and for survival for 10 years from the date of randomization. All patients must also be followed through completion of all protocol therapy, and until PD, even if they initiate non-protocol therapy.

6. Measurement of Effect

Definitions of Stringent Complete Response, Complete Response, Very Good Partial Response, Partial Response, and Stable Disease are based on International Uniform Response Criteria for Multiple Myeloma and the American Society of Hematology/Food and Drug Administration consensus panel recommendations for the assessment of disease progression.(64)

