7. QOL timepoints: At registration (+ 7 days) prior to initiation of treatment or observation; the last day (+ 7) of cycles 6, 12, 18, 24, 30, 36, 42, and 48; and at the end of treatment or observation (+14 days). For patients that discontinue protocol therapy or go off observation early not due to disease progression, QOL will also be assessed at the next quarterly Long Term follow-up visit (+ 14 days). After this, patients will not be followed further for QOL.
8. If leg swelling or pain is present in legs, an ultrasound of the legs will be done for deep vein thrombosis.
9. Bone marrow biopsy or aspirate performed to evaluate plasma cells %, presence of sheets of plasma cells and presence of plasma cell clonality. Absence of plasma cell clonality required for sCR.
10. Needed if urine M-spike at study entry was ≥ 200 mg/24 hr or if VGPR needs to be documented.
11. Patients will be followed for progression every 3 months if patient is < 2 years from study entry, every 6 months if patient is 2-5 years from study entry, every 12 months if patient is 6-10 years from study entry. No specific requirements if patient is more than 10 years from study entry. Patients will be followed for survival only once progression occurs and study treatment ends.
12. To be repeated every year or if clinically indicated for progression or symptoms.
13. To be assessed every 4 months.
14. All patients must be counseled about pregnancy precautions, risks of fetal exposure and other risks. The counseling must be done on Day 1 of each cycle (or at a minimum of every 28 days) and at drug discontinuation. The Lenalidomide Education and Counseling Guidance Document ([Appendix VII](#)) must be completed and signed by a trained counselor at the participating site prior to each dispensing of lenalidomide treatment. A copy of this document must be maintained in the patient records. A Lenalidomide Information Sheet ([Appendix VIII](#)) will be supplied to each patient receiving lenalidomide treatment. The patient must read this document prior to starting lenalidomide study treatment and each time they receive new supply of study drug.
- Rev. 8/11 15. Only enough lenalidomide for 28 days or one cycle of study treatment may be provided to the patient each cycle.
- Rev. 8/11 16. TSH should be tested for Arm A ONLY and then only when clinically indicated by the Principal Investigator.
-

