9.5 Secondary Clinical Endpoints

Secondary endpoints for this study include response rate and duration of response among responders. Response rate (CR+PR) on the R arm will be calculated and a 95% confidence interval will be computed around the response rate. The maximum width of a 95% confidence interval around response rate would be 21.5%. Duration of response among responders will be estimated using the Kaplan-Meier method.(65) Cox proportional hazards model will be used to assess PFS outcome in multiple regression analyses of established prognostic factors.(69) Adverse events will be monitored on all patients and summarized by arm. The difference in rates of all Grade 3 or higher toxicities will be evaluated for all randomized patients using the Fisher's Exact Test.

Overall Survival (OS) in each of the arms will be estimated using the method of Kaplan and Meier.(65) OS between the two arms will be compared using stratified log-rank test. (66) Cox proportional hazards model will be used to estimate the hazard rate between arms (69). OS will be evaluated at month 90/ year 7.5 when there is adequate power. The estimated 3-year survival probability on the R arm is supposed to parallel the probability for the general population of persons aged over 65 years (93%). The 3-year survival probability for an untreated high-risk SMM population is estimated at 83%.(23) Assuming exponential distributions, these probabilities correspond to a median OS of 28.7 and 11.2 years. For this analysis, we assume the R treated high-risk SMM population has a slightly inferior hazard of death than the general population: 3-year survival probability of 91% (hazard rate=0.0315). This estimate is

unchanged although the Spanish study reported 93% survival after approximately 5 years of follow-up (Mateos et al. Blood 2014). In the first report (Mateos et al. NEJM 2013), the 3-year survival on the watchful waiting arm of the Spanish study was 80%. In the long-term update, 5-year survival was 67% corresponding to a median OS of 9.2y on the watchful waiting arm. In this redesign, the 3-year OS estimate for the Obs arm was thus reduced to 79%. If OS follows an exponential distribution, this corresponds to medians of 22 years (R) and 8.8 years (Obs). There is 81% power to detect this difference assuming a one-sided 0.025 significance level and 47 events out of n=180 patients at the time of analysis.

Rev. 12/13

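### Section 5.2.7 leaves it unclear whether second cancers on observation must be reported, follow-up after progression does not look for them, and no time-adjusted comparison by arm is planned

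*Combined protocol and SAP*

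**What the plan says.** - **Risk.** Footnote 6 to the CAEPR (Section 5.3) says: "Patients treated with lenalidomide should be closely followed for the occurrence of SPMs".
- **Trigger.** Section 5.2.7 requires the Second Primary Form and a CTEP-AERS report for second malignancies, regardless of attribution, "that occur following treatment on NCI-sponsored trials must be reported as follows". Arm B is observation (Section 5.1.2), and no sentence says whether 5.2.7 covers it.
- **Wider NOTE in the same section.** "All new malignant tumors must be reported through CTEP-AERS whether or not they are thought to be related to either previous or current treatment". It states no arm limit.
- **End of reporting.** A later NOTE in 5.2.7 sets the stopping point: "Once data regarding survival and remission status are no longer required by the protocol, no follow-up data should be submitted via CTEP-AERS", and it applies the same limit to the Second Primary Form. Section 5.7 requires follow-up of all patients for response until progression "and for survival for 10 years from the date of randomization".
- **Follow-up schedule.** Section 7.1 footnote 11, for both arms: "Patients will be followed for survival only once progression occurs and study treatment ends". The study calendar has no second-malignancy item.
- **Analysis.** Section 9.5: "Adverse events will be monitored on all patients and summarized by arm". Grade 3 or higher rates are compared in all randomized patients by Fisher's exact test. Section 9 has no second-malignancy endpoint, cumulative incidence or exposure-adjusted rate.

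**The concern.** Lenalidomide is given until progression or toxicity to people without symptoms, so any added second cancers bear directly on benefit and risk. The randomized observation arm is the trial's only concurrent comparator for that question, and it helps only if cases are found and counted alike in both arms.

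Two features work against that. The opening sentence of 5.2.7 depends on treatment, and its NOTE does not, so two sites could reasonably treat an observation patient's new cancer differently. Active contact also shrinks at progression, which the plan expects much sooner on observation. Both push in the same direction: fewer cases found on observation at the same true risk. A crude comparison of proportions, the only kind of safety test in Section 9.5, does not correct for it. One of the reporting terms in 5.2.7 is a malignant neoplasm of grade 3 or 4, so these events could also enter the grade 3 or higher comparison.

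**Working it through.** **Inputs from Section 9.4.** Median PFS 24.8 months (Obs) and 62 months (R), exponential; 90 patients per arm; 45 months of accrual plus 9 of follow-up; full information at 76 events.

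**Input from Section 5.7.** Survival follow-up of 10 years (120 months).

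**Assumption.** The documents give no second-cancer rate. I take the same constant rate m in both arms, from 0.5% to 2% per year.

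**1. Reproduce the plan's figure.**
- Hazards: ln2/24.8 = 0.0279 and ln2/62 = 0.0112 per month, against 0.0279 and 0.011 stated.
- Expected events at T = 54 with uniform accrual over A = 45: 90 × [1 − (exp(−h(T−A)) − exp(−hT))/(hA)].
- Result: 50.2 (Obs) + 26.0 (R) = 76.2, against 76 stated. The hazards are a sound basis for the rest.

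**2. Mean progression-free time per patient**, (1 − exp(−hT))/h:

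| T (months) | R | Obs | R/Obs |
|---|---|---|---|
| 54 | 40.5 | 27.9 | 1.45 |
| 90 | 56.7 | 32.9 | 1.73 |
| 120 | 66.1 | 34.5 | 1.91 |

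The proportion still progression-free at 120 months, exp(−hT), is 26% on R and 3% on Obs.

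**3. Expected cases over 10 years at equal true risk**, 90 per arm, with m per month:
- Complete reporting for 10 years: 90 × (1 − exp(−120m)) in each arm (deaths ignored).
- Ascertainment ending at progression or death: 90 × m/(m+h) × (1 − exp(−120(m+h))).

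The last column of each table is the chance of a two-sided Fisher p<0.05 with the excess on R, from exact binomial enumeration.

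Complete reporting in both arms:

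| Assumed rate | R v Obs | p<0.05 against R |
|---|---|---|
| 0.5%/yr | 4.4 v 4.4 | 0.9% |
| 1%/yr | 8.6 v 8.6 | 1.5% |
| 2%/yr | 16.3 v 16.3 | 1.6% |

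Ascertainment ends at progression in both arms:

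| Assumed rate | R v Obs | Ratio | p<0.05 against R |
|---|---|---|---|
| 0.5%/yr | 2.4 v 1.3 | 1.90 | 1.1% |
| 1%/yr | 4.8 v 2.5 | 1.89 | 5.5% |
| 2%/yr | 9.2 v 4.9 | 1.87 | 15.1% |

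**4. Sensitivity to Arm B reporting.** If Arm A is fully reported for 10 years and Arm B only half, the ratio is 2.0 and p<0.05 against R occurs in 5% to 36% of trials over the same range of rates.

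**5. Person-time.** With a constant hazard and equal reporting, cases divided by observed person-years estimate the same rate in both arms whatever the follow-up length. The distortion in step 3 belongs to crude counts and proportions.

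**The case against.** The strongest reply is that the plan already requires what is asked. The NOTE in 5.2.7 covers all new malignant tumors and names no arm. The stopping rule in 5.2.7 is the end of survival and remission data, so the Second Primary Form remains due through the 10-year survival follow-up; footnote 11 sets a visit schedule and does not switch reporting off. Section 9 also speaks of treatment assignment for both arms, so the trigger might be read as covering either. Section 9.5 monitors adverse events in all patients by arm, the DMC reviews safety twice a year, and routine forms are defined in a Forms Packet that is not available here. Finally, a Fisher test on second cancers alone is an illustration, not an analysis in the plan.

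Much of this stands. A reader might infer from the opening of 5.2.7, and from the heading of the 5.2.6 table ("Last Dose of Investigational Agent (CC-5013/Lenalidomide) in this Study (Arm A) OR Within 30 Days" of the last dose of any protocol treatment), that observation patients are never reported. On that reading, with Arm A fully reported, 4.4 to 16.3 cases against 0 would be expected at equal risk, and p<0.05 would occur in 28% to nearly 100% of trials. The documents do not support it: the NOTE contradicts it, and the 5.2.6 table is a separate scheme. Nor do they support saying that reporting ends at progression, or that no comparable rate could be obtained.

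The reply does not resolve the differing scopes within 5.2.7, the lack of any described way to find cases at survival contacts, or the absence of a time-adjusted summary.

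**Conclusion.** The point holds as one of ambiguous coverage and unequal ascertainment. Comparable second-cancer data from the two arms are possible under the plan but not assured. If case finding in practice stops at progression, equal true risk would show as a crude excess of about 1.9-fold on lenalidomide at 10 years. A nominally significant Fisher result against lenalidomide would then occur in about 1% to 15% of trials, compared with 0.9% to 1.6% under complete reporting.

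These figures rest on the plan's exponential PFS hazards, a constant and equal second-cancer rate of 0.5% to 2% per year (assumed), and full reporting before progression in both arms. If reporting runs through survival follow-up in both arms, as 5.2.7 can be read, the ratio is 1.0. The actual bias cannot be fixed from the documents, since neither the second-cancer rate nor the completeness of Arm B reporting is given. The primary PFS analysis is unaffected. The changes are worth making because they are cheap and protect the trial's only randomized evidence on this risk.

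**What to change.** - **Section 5.2.7:** state that all second primary malignancies are reported in both arms from randomization (from registration for the non-randomized phase II patients), regardless of attribution or treatment received. This aligns the opening sentence with the NOTE.
- **Section 7.1, footnote 11:** change follow-up after progression from survival only to survival and second primary malignancy, through the existing 10 years, using the existing Second Primary Form at the existing contacts.
- **Section 9.5:** add cumulative incidence of second primary malignancy by randomized arm, with death as a competing event, and rates per person-year by arm. Include by-arm counts in the DMC safety reports.

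The cost is one question at contacts already planned, an existing form and a short addition to the analysis. If the Forms Packet already collects this in both arms, the collection change reduces to a clarifying sentence. The downside is modest data collection after progression, when later therapies may dilute the contrast between arms.
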